**Description:**

- The purpose of this RAP is to describe the planned analyses and output to be included in the Clinical Study Report for Protocol 201928.
- This RAP is intended to describe the pharmacodynamic/biomarker, safety, pharmacokinetic and efficacy analyses required for the study.
- This version of the RAP includes amendments to the originally approved RAP.
- This RAP will be provided to the study team members to convey the content of the Statistical Analysis Complete (SAC) deliverable.

## 1. INTRODUCTION

The purpose of this reporting and analysis plan (RAP) is to describe the analyses to be included in the Clinical Study Report for Protocol:

Revision Chronology:		
GlaxoSmithKline Document Number	Date	Version
2014N218070_00	2015-JUN-04	Original
2014N218070_01	2015-NOV-30	Amendment No. 1
Remove the specific equations for the prediction of percent predicted from spirometry from the inclusion criteria and in Section 7.7.2. At screening it may not be possible to identify which correction method was used, or modify the correction method used, at the time. It therefore is not valid to stipulate that lung function values be corrected using any particular method. Both FEV 1 and FVC measurements (which are not entry criteria for the study) collected during the study will be collected as absolute values (uncorrected), so that consistency will be obtained across all sites in the study, and percent predicted will be calculated using a standard approach in house at the end of the study.		
2014N218070_02	2016-JAN-26	Amendment No. 2
Increase the body mass index (BMI) range in the inclusion criteria from 18-32 kg/m  (inclusive) to 16- 35 kg/m  (inclusive). The original BMI range from 18-32 kg/m  is a typical range used in both healthy volunteer studies and general subject populations. The revised range is more appropriate for a COPD patient population.		
2014N218070_03	2016-NOV-16	Amendment No. 3
To remove photo toxicity from the protocol and to include minor administrative and clarification changes.		
2014N218070_04	2017-MAR-2	Amendment No. 4
Replace the administration of GSK2269557 via the DISKUS™ device (1000 µg) by a comparable dose administered via the ELLIPTA™ device (700 µg). GSK2269557 is no longer manufactured for use with the DISKUS device which will be replaced with ELLIPTA Device. To increase the number of patients to be recruited to obtain sufficient completers. Minor updates and clarifications.		

## 2. SUMMARY OF KEY PROTOCOL INFORMATION

### 2.1. Changes to the Protocol Defined Statistical Analysis Plan

Changes from the originally planned statistical analysis specified in the protocol are outlined in [Table 1](#).

**Table 1 Changes to Protocol Defined Analysis Plan**

Protocol	Reporting & Analysis Plan	
Statistical Analysis Plan	Statistical Analysis Plan	Rationale for Changes

 
Total lung capacity and lung lobar volumes included in HRCT secondary endpoint parameters
 
	
 
Total lung capacity and lung lobar volumes dropped from HRCT secondary endpoint parameters included as an exploratory endpoint parameter instead
 
	
 
The clinically relevant HRCT parameters are still to be decided. However, there was no clinical benefit seen in the comparison between GSK2269557 1000 mcg and Placebo in these parameters.
 

 
Analysis population:                             
 
All Subject All randomised subjects who receive at least one dose of the study treatment. This population will be based on the treatment the subject actually received.
 
Pharmacokinetic Subjects in the 'All subject' population for whom a pharmacokinetic sample was obtained and analysed.
 
 
 
	
 
Analysis population:                             
 
All Subject All randomised subjects who receive at least one dose of the study treatment. This population will be based on the treatment the subject actually received.
 
Pharmacokinetic Subjects in the 'All subject' population for whom a pharmacokinetic sample was obtained and analysed.
 
 
 
 
Note: The two subjects who were not compliant with inhaler instructions will be excluded from the outcome summaries if they received active treatment but will be included if they received placebo
	
 
2 subjects were not compliant with inhaler instructions and may not have received the full dose in amendment 4. Therefore, these subjects will be excluded from the outcome summaries if they received active treatment but will be included if they received placebo. Sensitivity analyses may be conducted including these subjects.
 

## 2.2. Study Objective(s) and Endpoint(s)

Objectives	Endpoints
Primary Objectives	Primary Endpoints

 
To establish the PI3K<math>\delta</math>-dependent changes in previously identified immune cell mechanisms specifically related to neutrophil function using mRNA in sputum from patients with an exacerbation of COPD, with or without treatment with GSK2269557.
 
	
 
Alterations in previously identified immune cell mechanisms specifically related to neutrophil function as determined by changes in mRNA transcriptomics in induced sputum after 12, 28 and 84 days of treatment.
 

Secondary Objectives	Secondary Endpoints

 
To evaluate the effect of once daily repeat inhaled doses of GSK2269557 on lung parameters derived from HRCT scans in subjects with acute exacerbation of COPD, compared to placebo.
 
	
 
Change from baseline in siVaw, iVaw, iRaw, siRaw, total lung capacity, lung lobar volumes, trachea length and diameter at FRC and TLC after 12 days of treatment and after 28 days of treatment.
 

 
To assess the safety and tolerability of once daily repeat inhaled doses of GSK2269557 administered to subjects with acute exacerbation of COPD, compared to placebo.
 
	
 
Adverse events
 
Haematology, clinical chemistry
 
Vital signs
 
12-lead ECG
 

 
To evaluate the plasma PK of once daily repeat inhaled doses of GSK2269557 administered to subjects with acute exacerbation of COPD.
 
	
 
Day 1 plasma Cmax and trough (24 hours) post dose for inpatients.
 
Trough concentration after 12 days, 28 days, 56 days and 84 days of treatment.
 

 
To evaluate the effect of once daily repeat inhaled doses of GSK2269557 on lung function parameters in subjects with acute exacerbation of COPD compared to placebo.
 
	
 
To evaluate the effect of once daily repeat inhaled doses of GSK2269557 on lung function parameters in subjects with acute exacerbation of COPD compared to placebo.
 

Exploratory Objectives	Exploratory Endpoints

 
To establish any other PI3K<math>\delta</math>-dependent changes in mRNA in sputum or blood from patients with an exacerbation of COPD, with or without treatment with GSK2269557.
 
To explore the pharmacodynamic effects in induced sputum of once daily repeat inhaled doses of GSK2269557 administered to subjects with acute exacerbation of COPD, compared to placebo.
 
	
 
To establish any other PI3K<math>\delta</math>-dependent changes in mRNA in sputum or blood from patients with an exacerbation of COPD, with or without treatment with GSK2269557.
 
To explore the pharmacodynamic effects in induced sputum of once daily repeat inhaled doses of GSK2269557 qPCR.
 

 
To assess the changes in other CT parameters such as low attenuation score after once daily repeat inhaled doses of GSK2269557 administered to subjects with acute exacerbation of COPD, compared to placebo.
 
	
 
Change from baseline for other CT parameters including low attenuation score after 12 days of treatment and after 28 days of treatment
 

### 2.3. Study Design

Overview of Study Design and Key Features	
Design Features	
 
• Multi-centre and Multi-Country
 
• Randomised
 
• Double-blind
 
• Placebo-controlled
 
• Parallel group
 

Dosing	
 
• Once daily, in the morning for 84 days
 
• Administered through the Diskus dry powder Inhaler
 

Time & Events	
 
• Refer to Appendix 2: Schedule of Activities
 

Treatment Assignment	
 
• Initially planned for approximately 30 subjects randomised to receive either 1000 µg GSK2269557 (Diskus) or matching Placebo in a 1:1 ratio as it was anticipated that 10 patients would drop-out. Twenty-eight subjects were randomised to this schedule, however, due to expiration date there was a protocol amendment following which additional subjects were subsequently randomised to receive either 700 µg GSK2269557 (Ellipta) or matching Placebo (Ellipta) in a 1:1 ratio. The protocol was updated such that approximately 45 subjects with an acute exacerbation of COPD would be randomized such that approximately 15 subjects on active and 15 subjects on placebo provide sputum at all the scheduled time points and complete the study.
 
• Subjects are assigned to treatment in accordance with the randomisation schedule generated by Clinical Statistics, using validated software.
 

Interim Analysis	
 
• No formal interim analysis will be conducted
 

## 2.4. Statistical Analyses

### 2.4.1. Primary Analyses

To estimate differences in mRNA intensities within and between treatment groups, a repeated measures model will be fitted to the results of the analysis of each probe set at Day 12, Day 28 and Day 84 following a loge transformation of the data. The Day 1 response will be fitted as a baseline covariate.

Back transformed ratios versus screening along with 95% confidence intervals will be calculated for each treatment group and timepoint. Additionally, baseline adjusted ratios of the change between active treatment and placebo will be calculated along with 95% confidence intervals.

Further details are provided in Section 7.1.

## 3. PLANNED ANALYSES

### 3.1. Final Analyses

The final planned primary analyses will be performed after the completion of the following sequential steps:

1. All participants have completed the study as defined in the protocol.
2. All required database cleaning activities have been completed and final database release (DBR) and database freeze (DBF) has been declared by Data Management.
3. All criteria for unblinding the randomisation codes have been met.
4. Randomisation codes have been distributed according to RandAll NG procedures.

## 4. ANALYSIS POPULATIONS

Population	Definition / Criteria	Analyses Evaluated
All Participants Enrolled (APE)	
 
• All subjects who were screened for eligibility
 
	
 
• Study Population
 

All Subjects	
 
• Comprised of all subjects who were randomised.
 
• This population will be based on the treatment the subject actually received.               
 
○ If participants receive >1 treatment, then they will be summarised according to the most frequently dosed treatment. In cases where the frequency is equal, the participant will be assigned the lowest dose strength of nemiralisib.
 
○ If participants receive no treatment, then they will be summarised according to "No Treatment"
 
 
 
	
 
• Study Population
 
• Pharmacodynamics and Biomarker
 
• Safety
 
• Efficacy
 

Pharmacokinetic (PK)	
 
• Subjects in the 'All Subjects' population for whom a pharmacokinetic sample was obtained and analysed.
 
	
 
• PK
 

Refer to [Appendix 10](#): List of Data Displays which details the population used for each display.

Note: The two subjects who were not compliant with inhaler instructions will be excluded from the outcome summaries if they received active treatment but will be included if they received placebo

#### 4.1. Protocol Deviations

During the course of the study it was noted that two subjects did not complete dosing instructions as required. The primary plan is if the subjects received active treatment they will be excluded from the study outcome summaries; if the subject received placebo treatment, they will be included in the study outcome summaries. It has not yet been identified if they received placebo or active treatment. A footnote will be applied to all relevant displays stating the rationale, subject number, treatment and if they were excluded, e.g. “Subjects X & Y did not complete dosing instructions as required; subject X received nemiralisib and was therefore excluded, subject Y received placebo and was therefore included.” The footnote may be tweaked for aesthetic purposes.

Important protocol deviations (including deviations related to study inclusion/exclusion criteria, conduct of the trial, patient management or patient assessment) will be summarised and listed.

Protocol deviations will be tracked by the study team throughout the conduct of the study in accordance with the Protocol Deviation Management Plan, refer to [Appendix 1](#).

- Data will be reviewed prior to unblinding and freezing the database to ensure all important deviations are captured and categorised on the protocol deviations dataset.
- This dataset will be the basis for the summaries and listings of protocol deviations.

A separate summary and listing of all inclusion/exclusion criteria deviations will also be provided. This summary will be based on data as recorded on the inclusion/exclusion page of the eCRF.

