### **7.2.3. Population of Interest**

The exploratory pharmacodynamic analyses will be based on the “All Subjects” population, unless otherwise specified.

As previously discussed for the two subjects that did not follow inhalation instructions, if the subjects received active treatment they will be excluded from the study outcome summaries; if the subject received placebo treatment, they will be included in the study outcome summaries.

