### **10. SAFETY ANALYSES**

The safety analyses will be based on the "All Subjects" population, unless otherwise specified.

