13.10.7. Pharmacokinetic Tables

Pharmacokinetic: Tables					
No.	Population	IDSL / Example Shell	Title	Programming Notes	Deliverable
Plasma Concentration					
4.1.	PK	PK01 PII116678/final/Table 4.1	Summary of Plasma Nemiralisib Pharmacokinetic Concentration – Time Data (ng/mL)	
All visits/timepoints, include a column for visit. Summarise PK data on original scale. Produce 95% CIs
 
Note: Use the separate NEMI Diskus and NEMI ELLIPTA treatment groups
 
Excluding the two subjects who were noted to not comply with inhalation instructions – include footnote
	SAC

Pharmacokinetic: Tables					
No.	Population	IDSL / Example Shell	Title	Programming Notes	Deliverable
4.2.	PK	PK01 PII116678/final/Table 4.2	Summary of Plasma Nemiralisib Pharmacokinetic Concentration – Time Data (ng/mL) Including All PK Concentrations Analysed	
All visits/timepoints, include a column for visit. Summarise PK data on original scale. Produce 95% CIs
 
Note: Use the separate NEMI Diskus and NEMI ELLIPTA treatment groups
 
Including the two subjects who were noted to not comply with inhalation instructions – include footnote
	SAC
4.3.	PK	PII116678/final/Table 4.3	Summary of Log-Transformed Plasma Nemiralisib Pharmacokinetic Concentration – Time Data (ng/mL)	
All visits/timepoints, include a column for visit and planned time. Summarise PK data on original scale. Produce n, No. imputed, geometric mean and corresponding 95% Cis SD Logs and %CVb
 
Note: Use the separate NEMI Diskus and NEMI ELLIPTA treatment groups
 
Excluding the two subjects who were noted to not comply with inhalation instructions – include footnote
	SAC

Pharmacokinetic: Tables					
No.	Population	IDSL / Example Shell	Title	Programming Notes	Deliverable
4.4.	PK	PII116678/final/Table 4.4	Summary of Log-Transformed Plasma Nemiralisib Pharmacokinetic Concentration – Time Data (ng/mL) Including All PK Concentrations Analysed	
All visits/timepoints, include a column for visit and planned time. Summarise PK data on original scale. Produce n, No. imputed, geometric mean and corresponding 95% Cis SD Logs and %CVb
 
Note: Use the separate NEMI Diskus and NEMI ELLIPTA treatment groups
 
Including the two subjects who were noted to not comply with inhalation instructions – include footnote
	SAC

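### Two inhaler-non-compliant subjects are dropped if on active but kept if on placebo, which can bias the All NEMI versus All Placebo comparison

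*SAP*

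**What the plan says.** Section 4.1 gives the primary plan for the two subjects: "if the subjects received active treatment they will be excluded from the study outcome summaries; if the subject received placebo treatment, they will be included". It adds: "It has not yet been identified if they received placebo or active treatment". Affected displays will carry a footnote naming each subject, the treatment and whether the subject was excluded.

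The rule recurs in three other places:

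- **Section 2.1, Table 1** gives the reason, which is that the subjects may have received less than the full dose. On the inclusive analysis it says only: "Sensitivity analyses may be conducted including these subjects".
- **Section 4** has a note that the two subjects "will be excluded from the outcome summaries if they received active treatment but will be included if they received placebo". It stands under the table defining All Subjects ("This population will be based on the treatment the subject actually received"), the population used for PD/biomarker, efficacy and safety.
- **Section 7.2.3** repeats the rule for exploratory PD, starting "As previously discussed for the two subjects that did not follow inhalation instructions".

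Section 7.1.3 bases the primary PD analysis on All Subjects. Section 5.1 makes All NEMI versus All Placebo the PD and efficacy comparison.

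The list of displays treats the endpoints differently. For PK (13.10.7), Tables 4.1 and 4.3 exclude the two subjects, and Tables 4.2 and 4.4 are marked "Including the two subjects who were noted to not comply with inhalation instructions". Table 6.1 (primary sputum mRNA) and Tables 2.51-2.54, 2.62 and 2.64 (secondary efficacy models) have one version each.

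**The concern.** The reasoning behind the rule covers dose only: a missed active dose dilutes the effect, while a missed placebo dose loses nothing. But failure to follow inhaler instructions is also patient behaviour, and it may go with a different outcome for reasons unrelated to the drug. If it does, the placebo mean keeps such subjects and the active mean does not. The arms then differ by a selection applied after randomisation, not only by treatment.

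The arms are small, so one subject carries visible weight. The reader may also never see the analysis without the selection, because outside PK the SAP does not commit to it.

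A second, smaller problem is scope. The SAP does not define outcome summaries. Section 10 states "The safety analyses will be based on the" All Subjects population and mentions no exclusion, yet the Section 4 note sits under a population that also serves safety. A programmer could read it as removing a dosed active subject from the adverse event tables.

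**Working it through.** The SAP states no figure for the effect of this rule, so there is none to reproduce.

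**Inputs from the SAP**
- Two non-compliant subjects, treatment unknown (Section 4.1).
- 1:1 allocation (Section 2.3).
- About 15 subjects per arm completing with sputum at all time points, and about 45 randomised, i.e. about 22 per arm (Section 2.3).

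**Assumption:** non-compliers differ from other subjects by z = 1 to 2 SD, in either direction.

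**Allocation.** Let k be the number of the two on active. Under 1:1 allocation k is binomial(2, 0.5), so P(0) = 0.25, P(1) = 0.50 and P(2) = 0.25. At least one is on active with probability 0.75.

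**Expected active minus placebo difference under no drug effect, n per arm**

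| k | Probability | SAP rule: -(2-k)z/n | Keep both: (2k-2)z/n | Exclude both |
|---|---|---|---|---|
| 0 | 0.25 | -2z/n | -2z/n | 0 |
| 1 | 0.50 | -z/n | 0 | 0 |
| 2 | 0.25 | 0 | +2z/n | 0 |
| Average | | **-z/n** | **0** | **0** |

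When both subjects are kept, the negative and positive shifts cancel over the allocation. The SAP rule keeps the first and deletes the second.

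**Size of the average shift**, with SE of the difference = sqrt(2/n) SD

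| n per arm | SE (SD) | z = 1 | z = 2 |
|---|---|---|---|
| 15 | 0.365 | 1/15 = 0.067 SD = 0.18 SE | 2/15 = 0.133 SD = 0.37 SE |
| 22 | 0.302 | 1/22 = 0.045 SD = 0.15 SE | 2/22 = 0.091 SD = 0.30 SE |

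At z = 0.5 the average shift is 0.033 SD (n = 15) or 0.023 SD (n = 22), under 0.1 SE. At z = 0 it is zero.

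**Simulation** (100,000 trials, unadjusted two-sided 5% t-test, no drug effect)
- SAP rule: mean shift 0.067 and 0.132 SD (n = 15; z = 1, 2) and 0.045 and 0.092 SD (n = 22). Type I error was 5.1% and 5.4%, and 5.2% and 5.5%.
- Both kept or both excluded: mean shift within 0.003 SD of zero, type I error 4.8 to 5.0%.

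**Cost of keeping an under-dosed active subject.** If no drug at all was delivered to k active subjects, the effect shrinks by k/n. That is 6.7% or 13.3% (k = 1, 2; n = 15) and 4.5% or 9.1% (n = 22). With k = 2, a true 1.5-fold change becomes 1.5^(1-2/15) = 1.42 or 1.5^(1-2/22) = 1.45.

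**The case against.** The strongest defence is that this is a documented choice based on exposure. The objective is PI3Kδ-dependent change, under-delivery matters only where there is drug to deliver, the rule was fixed blind to arm, and it will be footnoted. Blinding does rule out a choice driven by results, and whether to accept dilution is partly a question of estimand. But excluding both subjects whatever their arm would remove the dilution equally well without treating the arms differently.

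Second, in half of allocations the planned analysis coincides with a symmetric one: both kept if both are on placebo, both excluded if both are on active. Only the 50% case of one in each arm is peculiar to the rule. The table also gives a mean-square shift of 1.5(z/n)² for the rule (0.25 × 4 + 0.50 × 1) against 2(z/n)² for keeping both (0.25 × 4 + 0.25 × 4). This is correct. However, the shift from keeping both is ordinary chance imbalance centred on zero, whereas the rule's shift has a non-zero mean.

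Third, the gap of 1 to 2 SD has no source in the SAP, and the simulation ignores baseline. The planned models use it: Screening is a visit in Section 7.1.4.1, and baseline terms appear in 8.1.4.1 and 8.2.4.1. A gap already present at baseline would be at least partly adjusted away, so the figures may overstate the shift. The primary output is also a set of estimates and unadjusted p-values for 638 probe sets, not one confirmatory test. All of this limits the size of the problem but does not remove the asymmetry.

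**Conclusion.** The concern holds and should be fixed. In the PD and efficacy comparisons, the same deviation is handled differently by arm, and the analysis without that difference is optional except for PK.

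The effect is modest and falls mainly on the estimate: on average 0.05 to 0.13 SD, or 0.15 to 0.37 SE, across 15 to 22 per arm, with little change in type I error. This rests on 1:1 allocation of the two subjects, an assumed gap of 1 to 2 SD and no baseline adjustment. The sign depends on the endpoint and has no single direction across the 638 probe sets. If non-compliers do not differ in outcome, there is no bias.

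The safety point is an ambiguity of wording, not a stated exclusion.

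**What to change.** Before unblinding, replace the rule in Sections 2.1, 4, 4.1 and 7.2.3 with text such as:

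> In the primary PD and efficacy analyses, both subjects stay in the treatment group given by the All Subjects population (treatment actually received), whichever arm that is. A sensitivity analysis excluding both subjects regardless of treatment will be produced for the primary sputum mRNA endpoint (companion to Table 6.1) and the secondary efficacy endpoints (companions to Tables 2.51-2.54, 2.62 and 2.64).

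Add to Section 4:

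> The term outcome summaries does not cover safety displays; no dosed subject is removed from the displays in 13.10.6.

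Tables 6.2 and 6.3 follow the same inclusion rule through the change to 7.2.3. Merely making the inclusive analysis mandatory would close the reporting gap but leave the primary comparison asymmetric.

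The cost is SAP wording and one rerun of the listed models. The downside is the dilution shown above if an active subject was under-dosed: at worst 4.5 to 6.7% of the effect with one such subject and 9.1 to 13.3% with two. The companion analysis makes that visible.
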